## Abbreviations

| Abbreviation | Definition                                   |
|--------------|--|
| ACQ          | Asthma Control Questionnaire                 |
| ALT          | alanine aminotransferase                     |
| AST          | aspartate aminotransferase                   |
| ATS          | American Thoracic Society                    |
| BMI          | body mass index                              |
| BTS          | British Thoracic Society                     |
| CCL          | chemokine ligand                             |
| CQLQ         | Cough specific quality of life questionnaire |
| CT           | computed tomography                          |
| CRF          | case report form                             |
| ERS          | European Respiratory Society                 |
| FAS          | Full-analysis set                            |
| FeNO         | fractional exhaled nitrous oxide             |
| FEV1         | forced expiratory volume in 1 second         |
| FVC          | forced vital capacity                        |
| GCP          | Good Clinical Practice                       |
| GINA         | Global Initiative for Asthma                 |
| ICF          | informed consent form                        |
| ICS          | inhaled corticosteroids                      |
| LCM          | Leicester Cough Monitor                      |
| LCQ          | Leicester Cough Questionnaire                |
| MiniAQLQ     | Mini asthma quality of life questionnaire    |
| EC           | Ethics committee                             |
| Ig           | immunoglobulin                               |
| IL           | interleukin                                  |
| LABAs        | long-acting $\beta$ -2 agonists              |
| OCS          | oral corticosteroids                         |
| OTC          | over the counter                             |
| PRO          | patient-reported outcome                     |
| SABAs        | short-acting $\beta$ -2 agonists             |
| SAP          | Statistical analysis plan                    |
| T2           | Type-2 eosinophilic inflammation             |
| TB           | tuberculosis                                 |

## 1.0 Background

### 1.1 Cough and Asthma

Asthma is a respiratory disease that affects 1-18% of the worldwide population. It is characterised by a collection of symptoms which include shortness of breath, chest tightness, wheeze and cough and by variable expiratory airflow limitation. These usually tend to vary over time and in intensity and can be triggered by a range of stimuli.(1) The condition is typically recognised as one that consists of periodic exacerbations coupled with chronic inflammation of the airways with or without structural airway changes. This may also be associated with persistent symptoms and a reduced lung function.(2)

Asthma has been traditionally 'stratified' on the basis of response to 'step-wise' incremental treatment with inhaled corticosteroid (ICS) therapy forming the cornerstone of this approach (1,3). However, more recently, asthma has been stratified on the basis of inflammatory phenotype to better understand disease heterogeneity with a view to developing biomarkers of therapeutic response and for the better targeting of both new and existing treatments (4,5). Using sputum analysis (5,6), and more recently whole genome expression profiling (4), it is clear that even in mild steroid-naïve asthma, approximately 50% of patients do not have a typical Type 2 (T2)-driven eosinophilic inflammation, and are called 'T2-low asthma'. Perhaps more significantly, based on the normal diagnostic criteria for asthma, this T2 low group is indistinguishable from the typical 'T2-high'/eosinophilic group. In the context of therapeutic response, the T2-low patients have a minimal response to ICS therapy (5,6). In severe disease, the T2-low profile is also prevalent (7,8), and in case series of difficult-to-treat patients with asthma, there is evidence that inappropriate escalation of corticosteroid treatment is frequent, with significant morbidity due to systemic corticosteroid exposure (9-11). The RASP-UK programme is exploiting the use of composite biomarkers of T2 biology to define patient sub-groups using easily measurable biomarkers (blood eosinophil count, fractional exhaled nitric oxide (FeNO) and serum periostin) (<http://www.rasp.org.uk/>)

Despite its troublesome occurrence in disease, cough is important in normal human health in maintenance of the respiratory system. Its role in removal of foreign material and in enhancing mucociliary clearance helps to protect the airways when stimulated by extrinsic factors or in the presence of disease.(12) Cough becomes disordered in asthma and is thought to be due to the associated inflammation in the lungs, which causes sensitisation of cough reflexes and can lead to upsetting attacks of cough due to minimal stimulation or changes in the environment.(13)

Cough is one of the main reported symptoms in asthma. Although symptoms such as wheeze and shortness of breath may be more prevalent in the condition, cough in asthmatic patients is often described as the most problematic.(14) It is therefore surprising that although there are a number of tools available to aid in management of cough (15), there has been little consideration given to the assessment how severe a patient's cough is in asthma.

When a patient's cough is poorly controlled, it tends to drive escalation of corticosteroid therapy. This is not always appropriate and often fails to achieve adequate disease control and often unnecessarily exposes patients to the unacceptable side effects of high dose corticosteroid therapy. A novel approach has been developed to manage patients

and their treatment based on individual inflammatory biomarker profiles. Only half of patients with asthma have typical eosinophilic airway inflammation driven by 'Type 2' cytokines (interleukin IL-4, IL-5 and IL-13). In severe asthma, this proportion drops to between 25-50%. For the remainder of patients there is little evidence that T2 cytokines play a major role in their condition and so respond less well to steroid therapy. These patients have been termed 'T2-Low'.

Therefore, it is important to accurately define how cough is related to the clinical and biological phenotypes in asthma.

## 1.2 Study Rationale

We hypothesise that cough represents a significant burden in severe asthma which can be defined using subjective and objective cough measures. It is also hypothesised that cough morbidity is over-represented in the T2-low severe asthma population and this may represent mechanistic pathways that are suitable for exploitation for novel anti-tussive drug discovery.

This study will use a combination of subjective and objective cough measures to assess the frequency of cough as well as its related morbidity in severe asthmatics. Comparisons will be made between T2-High, T2-Low and T2-intermediate patients defined using a composite biomarker profile (blood eosinophil count and FeNO) to assess the role of cough in each and these results will be compared to the transcriptomic and proteomic measurements in the RASP-UK where the same biomarker profiling is being used to define clinical sub-groups of severe asthma. This study aims to also improve characterisation of the T2-Low population and identify possible mechanisms for the pathophysiology of this group.

A population of patients will be assessed after screening at a single visit to enable the summary of clinical characteristics and allow these data to be related to the biomarkers measured in serum, plasma and sputum.

Four patient groups will be investigated in the study and will be defined as follows:

### Group A

#### T2-High Severe Asthmatics

- Persistent blood eosinophil count  $\geq 0.3 \times 10^9/\text{mL}$  **and**
- Persistent high FeNO levels  $\geq 30 \text{ ppb}$  **and**
- Adherence to inhaled and oral corticosteroid therapy

### Group B

#### T2-Low Severe Asthmatics

- Persistent blood eosinophil count  $\leq 0.2 \times 10^9/\text{mL}$  **and**
- Persistent low FeNO levels ( $< 30 \text{ ppb}$ )

These measurements are undertaken routinely at each clinic visit at the Difficult Asthma Service in Belfast HSC Trust.

## Group C

### Mild/moderate Asthmatics

- mild/moderate severe asthmatics (defined as step 2/3 using the GINA classification of severity) recruited from general respiratory clinics in the Belfast HSC Trust

## Group D

### T2 – intermediate

- Persistent blood eosinophil count  $\geq 0.3 \times 10^9/\text{mL}$  OR
- Persistent FeNO levels  $\geq 30 \text{ ppb}$

We believe that these patient groups will show differences in their cough frequency and severity and this novel research may provide information that will help to further characterize these phenotypes in the future. We believe that cough as a symptom in asthma is independent of Type-2 inflammation pathways and so further research into this symptom may help to uncover alternative pathways driving the condition. We aim to understand cough in relation to specific biomarkers in this population and how differences in cough frequency and severity relates to them. It is important to understand the nature of cough in these patients and how it changes in response to treatment.

## **2.0 Objectives**

### **2.1 Primary Objectives**

The primary objectives for this study are as follows:

- To objectively measure cough frequency in different phenotypes of severe asthma (T2-high, T2-low and T2-intermediate) and a mild/moderate asthma control group using a validated ambulatory cough monitor (Leicester Cough Monitor)
- To objectively measure cough reflex sensitivity in different phenotypes of severe asthma and a mild/moderate asthma control group using citric acid cough challenge testing
- To subjectively measure cough severity and quality of life in different phenotypes of severe asthma and a mild/moderate asthma control group using the Leicester cough questionnaire (LCQ), Cough Quality of life Questionnaire (CQLQ) and visual analogue scales

### **2.2 Exploratory Objectives**

The exploratory objectives for this study are as follows:

- To determine the relationship between objective and subjective measures of cough and established biomarkers of asthma severity and symptom control including sputum eosinophils (as defined by % eosinophils), blood eosinophil count, FeNO (ppb), lung

function (FEV1), and Asthma Control Questionnaire (ACQ-5).

- Exploratory analysis will be undertaken to determine the relationship between the objective and subjective cough measures, biomarker profile and transcriptomic and proteomic measurements in blood and urine samples from severe asthma patients using learning from the RASP-UK programme in relevant stored samples.
- Reproducibility of objective and subjective measures of cough in a severe asthma population will also be explored.

## 2.3 Description of Study

This is a cross-sectional study, in patients aged 18 to 75 years (inclusive), with severe asthma, as defined by the GINA step 4/5 classification of asthma severity (1). Prior to screening, patients will have been assessed using a systematic protocol to exclude other causes of apparently uncontrolled asthma (16). It is expected that approximately 60 patients will be enrolled at the study centre. Following review after clinical attendance, patients will be invited to take part in the study and attend for a screening visit. Patients will be provided with an information sheet and have a telephone follow-up after at least 24 hours to ask if they remain interested in participation and if so, they will then be asked back for a baseline visit.

## 3.0 Patient and Methods

### 3.1 Patients with severe asthma (Groups A, B and D)

The study will recruit patients aged 18 to 75 years, inclusive, with severe OCS-dependent asthma (GINA step 5 classification of asthma severity).

#### 3.1.1 Inclusion Criteria

Patients must meet the following criteria for study entry:

1. Ability and willingness to comply with the study procedures
2. Age  $\geq 18$  to  $\leq 75$  years at the time of informed consent
3. Severe asthma (as defined by GINA step 4/5 classification of asthma severity) after a detailed systematic assessment
4. History of asthma treatment with high doses of ICS ( $\geq 1000$   $\mu$ g beclomethasone dipropionate daily, or equivalent) and an additional controller
5. Three patient groups with severe asthma will be investigated in the study and will be defined as follows:

#### T2-High Severe Asthmatics (Group A)

- Persistent blood eosinophil count  $\geq 0.3 \times 10^9/\text{mL}$  **and**
- Persistent high FeNO levels  $\geq 30$  ppb **and**

- Adherence to inhaled and oral corticosteroid therapy

**T2-Low Severe Asthmatics (Group B)**

- Persistent blood eosinophil count  $\leq 0.2 \times 10^9/\text{mL}$  **and**
- Persistent low FeNO levels ( $< 30 \text{ ppb}$ )

**T2 – Intermediate Severe Asthmatics (Group D)**

- Persistent blood eosinophil count  $\geq 0.3 \times 10^9/\text{mL}$  OR
- Persistent FeNO levels  $\geq 30 \text{ ppb}$

As stated above, these measurements are made at each clinic visit as part of routine care and will be available on all subjects prior to Inclusion

6. A chest x-ray or CT scan obtained within 12 months before the time of informed consent and showing no new pathology requiring investigation as a potential cause for their cough

### **3.1.2 Exclusion Criteria**

Patients who meet any of the following criteria will be excluded from study entry:

1. Baseline FEV1  $\leq 50\%$  of predicted or  $\leq 1.0\text{L}$
2. Asthma exacerbation within 28 days before the time of informed consent or during Screening
3. Major episode of infection requiring any of the following:
  - Admission to hospital for  $\geq 24$  hours within the 28 days before the time of informed consent
  - Treatment with intravenous antibiotics within the 28 days before the time of informed consent or during Screening
  - Treatment with oral antibiotics within the 14 days before the time of informed consent or during Screening
4. For adults: Active tuberculosis (TB) requiring treatment within the 12 months before the time of informed consent (patients are also required to have no recurrence of symptoms in the 12 months following completion of TB treatment), or
5. Known history of severe clinically significant immunodeficiency, including, but not limited to, human immunodeficiency virus infection and/or currently receiving or have historically received intravenous Ig for treatment for immunodeficiency  
 Note: Immunodeficiency encompasses a wide spectrum of human conditions and/or diseases. A relative IgG deficiency that is thought, but not proven, to be a feature of severe asthma would not be exclusionary for the study.
6. Diagnosis or history of malignancy, or current investigation for possible malignancy
7. Other clinically significant medical disease that is uncontrolled despite

treatment or that is likely, in the opinion of the investigator, to require a change in therapy or affect the ability to participate in the study

8. History of alcohol, drug, or chemical abuse that would impair or risk the patient's full participation in the study, in the opinion of the investigator
9. Current smoker or former smoker with a smoking history of >15 pack-years

A current smoker is defined as someone who has smoked one or more cigarettes per day (or marijuana or pipe or cigar) for  $\geq 30$  days within the 24 months before the time of informed consent and for whom cotinine testing is positive.

A former smoker is defined as someone who has smoked one or more cigarettes per day (or marijuana or pipe or cigar) for  $\geq 30$  days in his or her lifetime (as long as the 30-day total did not include the 24 months before the time of informed consent) and for whom cotinine testing is negative.

A pack-year is defined as the average number of packs per day times the number of years of smoking.
10. Initiation of or change in allergen immunotherapy within three months before the time of informed consent
11. Treatment with an investigational agent within 30 days of informed consent or 5 half-lives of the investigational agent, whichever is longer
12. Female patients who are pregnant or lactating

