### **3.2 Control Population (Group C)**

Mild/moderate severe asthmatics (who have received a diagnosis of asthma from a physician and are defined as step 2/3 using the BTS/SIGN classification of severity and ACQ<1.5) aged 18-75 years inclusive will be recruited from general respiratory clinics in the Belfast HSC Trust. Patients must have the ability and willingness to comply with study procedures.

Patients within this population will also be recruited through selected General Practice surgeries. Patients attending general asthma review clinics within their surgery will be approached by practice nurses and informed about the study and given the appropriate study information (patient information sheet, invitation letter from GP surgery etc). Patients may then contact the study coordinator if interested in taking part in the study.

Exclusion criteria for this group is as detailed in section 3.1.2.

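### The infection exclusion reaches only infections that led to admission or antibiotics, so cough from an untreated respiratory infection may enter the cough counts, cough questionnaires and VAS

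*Combined protocol and SAP*

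**What the plan says.** Criterion 3 of section 3.1.2 opens with "Major episode of infection requiring any of the following" and then gives three triggers. The first is a hospital stay of a day or longer in the 28 days preceding consent. The second is intravenous antibiotics, also with a 28-day reach. The third, for oral antibiotics, has a shorter reach: "Treatment with oral antibiotics within the 14 days before the time of informed consent or during Screening".

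Two neighbouring criteria could catch some infections. Criterion 2 is "Asthma exacerbation within 28 days before the time of informed consent or during Screening"; the protocol does not define an exacerbation. Criterion 7 leaves room for judgement: it takes in other significant illness that treatment has not controlled, or that the investigator expects to call for new therapy or to interfere with taking part. For the mild/moderate controls, section 3.2 says "Exclusion criteria for this group is as detailed in section 3.1.2", so all four groups share the list.

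Cough is what the study measures. The first primary objective (section 2.1) is "To objectively measure cough frequency in different phenotypes of severe asthma" and in the controls, using a 24-hour monitor recording. The second is citric acid reflex sensitivity. The third is cough severity and quality of life by LCQ, CQLQ and visual analogue scales. Section 4.2 analyses every patient who satisfies the entry criteria. Sections 4.3 and 4.4 do not mention acute infection.

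**The concern.** The study wants to attribute differences in cough to asthma phenotype. Acute respiratory infection is a common cause of transient cough unrelated to phenotype, yet the exclusion depends on the care the infection received and not on whether the patient is coughing from it. Someone with a five-day-old cold, no antibiotic and no exacerbation meets none of the three triggers.

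Two things are at stake. The first is the group summaries and comparisons at Visit 1, which rest on one 24-hour recording and a 2-week questionnaire recall in about 60 patients. The second is the reproducibility objective in the 25 patients seen again two weeks later: an infection that starts or clears between visits would look like poor repeatability of the measures.

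**Working it through.** **1. Does anything else close the gap?**

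| Provision | Reaches an untreated cold or chest infection? |
|---|---|
| Criterion 2, exacerbation, 28 days | Only if it is judged an exacerbation |
| Criterion 7, other disease | Discretionary; a self-limiting cold does not plainly meet it |
| Chest film (3.1.1, item 6) | No; it may be 12 months old and is listed only for the severe groups |
| Prior systematic work-up (2.3) | No; done before screening and aimed at uncontrolled asthma |
| ACQ below 1.5 for Group C (3.2) | No; none of the five ACQ items asks about cough |
| Visit 1 history, temperature, examination (3.4) | May reveal it, but no rule acts on the finding |

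At Visit 2, Table 1 schedules neither an eligibility check nor concomitant medications. Adverse events are assessed, but Table 2 limits them to events caused by research procedures, so an intercurrent cold has no scheduled place in the record.

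**2. Which outcomes, and in which direction?** The monitor counts cough whatever its cause. LCQ items ask about cough over 2 weeks without asking why, and are scored from 1 (worst) to 7 (best), so infective cough lowers the LCQ. CQLQ items are adverse statements, so infection moves answers towards agreement, taken here as the higher score. The cough VAS runs from 0 mm to 100 mm (worst). The citric acid challenge measures reflex sensitivity and does not count spontaneous cough. An effect of infection on it is plausible, but the documents do not state one.

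**3. How often?** The plan gives no group sizes and no sample size calculation, so there is no figure to reproduce. Assume equal groups, 60/4 = 15, and a share p of patients affected at a visit. P(at least one of n) = 1 − (1 − p)^n.

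| p (assumed) | Expected of 60 | At least 1 of 15 | At least 2 of 15 | At least 1 of 25 |
|---|---|---|---|---|
| 2% | 1.2 | 26% | 3.5% | 40% |
| 5% | 3 | 54% | 17% | 72% |
| 10% | 6 | 79% | 45% | 93% |
| 15% | 9 | 91% | 68% | 98% |

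**4. How large, if the infections fall in one group only?** Assume 2 of 15 are affected, with counts multiplied by k, a log-scale summary and an SD of 0.5 log10. None of these is in the documents.

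- Geometric mean ratio = k^(2/15): 3^(2/15) = 1.16 and 10^(2/15) = 1.36.
- Shift in log10 = (2/15) × log10 k: 0.06 for k = 3 and 0.13 for k = 10.
- SE of a two-group difference = 0.5 × √(2/15) = 0.18.
- Shift/SE: 0.0636/0.1826 = 0.35 and 0.1333/0.1826 = 0.73.

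**5. And if infection is equally common in both groups?** The expected shift cancels and variance rises by p(1 − p)(log10 k)². With p = 2/15:

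- k = 3: 0.1156 × 0.2276 = 0.026; SD = √(0.25 + 0.026) = 0.53; SE = 0.53 × √(2/15) = 0.19.
- k = 10: 0.1156 × 1 = 0.116; SD = √(0.25 + 0.116) = 0.60; SE = 0.60 × √(2/15) = 0.22.

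**6. Reproducibility.** One patient infected at only one of the two visits adds a within-pair difference of log10 3 = 0.48 to log10 10 = 1.00.

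**The case against.** The strongest reply is that the effect is small and mostly not bias. Every group uses the same exclusions, and the documents give no reason to expect infection to be commoner in one phenotype. With equal rates the comparisons lose some precision and little else. Even when all the assumed infections are put in one group, the shift stays below one standard error. The study also describes itself as exploratory. All of that stands, and it limits the weight of the point. Group C is recruited by a different route (general respiratory clinics and general practices), so a seasonal difference is possible, but nothing says it will occur.

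A second reply is that an infected patient might be noticed anyway. The Visit 1 assessments could reveal an infection, criterion 7 allows discretion, and the citric acid challenge follows a centre protocol that is not in the documents and may defer such patients. This also stands as far as it goes. It makes enrolment of these patients possible, not certain, but it supplies no rule for the monitor, questionnaires or VAS.

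A reader might also infer that the 14-day oral-antibiotic window is an error, because the other windows are 28 days. The documents do not support that. Different windows can reflect different severity, and 14 days matches the 2-week LCQ recall.

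**Conclusion.** The point holds as a gap in eligibility and data capture that is cheap to close. As written, the plan may admit patients with untreated respiratory infection and has no means of separating their cough from asthma cough in the monitor counts, LCQ, CQLQ and VAS, or in the Visit 2 repeat data.

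Three stronger readings go too far:

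- That every such patient is eligible: criteria 2 and 7 will remove some.
- That all primary outcomes are affected in the same way: the citric acid effect is not documented, and the LCQ moves down while the others move up. The Cough Hypersensitivity Questionnaire is not named in the primary objectives.
- That the phenotype comparison is biased: this requires infection to differ by group or season, which the documents neither show nor exclude.

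The illustrative size is 0.06 to 0.13 log10 (0.35 to 0.73 of a standard error) if 2 of 15 patients in one group only are affected. With equal rates of 2 in 15, the standard error rises from 0.18 to between 0.19 and 0.22. Group size, number affected, fold increase and SD are all assumptions. The gap itself rests on the text alone.

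**What to change.** **Visit 1.** Add to section 3.1.2 a deferral for symptomatic upper or lower respiratory tract infection, treated or untreated, within a stated window before Visit 1. The window should at least cover the 2-week LCQ recall; the 28 days already used for exacerbation is one option. Ask the question at booking and rebook once the window has passed, so that the patient is deferred and not lost. Leave the oral-antibiotic window as it is.

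**Visit 2.** Ask about and record any new respiratory infection since Visit 1, and state in section 4.4 that reproducibility will be reported with and without those patients. A 28-day deferral here would be counterproductive: it could move Visit 2 from Day 15 to about Day 43 (15 + 28) and mix retest intervals among only 25 patients.

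**Cost.** One eligibility line, one question at each visit and one extra reproducibility summary. Some Visit 1 bookings will be delayed by a few weeks. No study procedure is added.
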